6.2.2 EVALUATION FOR DOSE-LIMITING TOXICITY, PHASE I ONLY

Subjects will be evaluated for toxicity according to the Common Terminology Criteria for Adverse Events (CTCAE) of the National Cancer Institute (NCI) version 4.0 (Appendix A).

A DLT is defined as any of the below treatment emergent toxicities **with attribution (possibly, probably or definitely related) to one or more of the study drugs** that occur during Cycle 1. Toxicities that occur in subsequent cycles will be handled through dose modifications (Section 6.3) but will not figure into the definition of MTD. Patients will be considered evaluable for DLT if they receive the assigned doses and schedule of chemotherapy throughout Cycle 1 or develop a DLT. If a patient does not develop a DLT, but does not complete Cycle 1 for any reason, then that patient will be considered not evaluable for DLT and be replaced.

Non-hematologic:

- \geq *Grade 2 neuropathy with pain*
- \geq Any Grade 3 or 4 adverse event (excluding grade 3 nausea, vomiting, diarrhea lasting < 7 days or grade 3 fatigue).
- \geq Grade 3 nausea, vomiting, or diarrhea lasting \geq 7 days despite maximal antiemetic/antidiarrheal therapy
- Grade 5 toxicity

Note: Abnormal non-hematologic laboratory values \geq grade 3 will be considered a DLT if they are determined to be clinically significant (i.e. result in dose interruption, delay or dose modification during cycle 1 or in a significant side effect as determined by the investigator) and possibly, probably or definitely related to study drug. If baseline value is elevated (or decreased) prior to enrollment, an increase (or decrease) will not be considered a DLT unless it worsens by 2 grades and is determined to be clinically significant by the treating investigator.

Hematologic:

- Grade 4 neutropenia (ANC < 0.5 x $10^{9}/L$) lasting for \geq 7 days
- Febrile neutropenia (ANC < $1.0 \times 10^{9}/L$ with a fever $\geq 38.3^{\circ}C$)
- Grade 4 thrombocytopenia (platelets $< 25.0 \times 10^{9}/L$) lasting ≥ 7 days despite dose delay
- Grade 3-4 thrombocytopenia associated with bleeding
- Grade 5 toxicity

6.2.3 DOSE ESCALATION SCHEME - FOR PHASE I ONLY

Dose escalation will proceed within each cohort according to the following scheme. Dose-limiting toxicities (DLT) are defined above.

Number of Subjects with DLT at a Given Dose Level	Escalation Decision Rule
0 out of 3	Enter 3 subjects at the next dose level.
> 2	Dose escalation will be stopped. This dose level will be declared the maximally administered dose (highest dose administered). Three (3) additional subjects will be entered at the next lowest dose level if only 3 subjects were treated previously at that dose.
1 out of 3	 Enter at least 3 more subjects at this dose level. a. If 0 of these 3 subjects experience DLT, proceed to the next dose level. b. If 1 or more of this group suffer DLT, then dose escalation is stopped, and this dose is declared the maximally administered dose. Three (3) additional subjects will be entered at the next lowest dose level if only 3 subjects were treated previously at that dose.
≤ 1 out of 6 at highest dose level below the maximally administered dose	This is generally the recommended phase II dose. At least 6 subjects must be entered at the recommended phase II dose.

6.2.4 PHASE II PORTION OF THE STUDY

AGENT	DOSE	ROUTE	DAYS	INTERVAL
Irinotecan	125 mg/m ²	IV infusion (over 90 min)	1, 8, 15	q 28 days
Carfilzomib	20/36 mg/m ²	IV infusion (over 30 min)	1, 2, 8, 9 15 and 16	q 28 days

* Cycle 1 Day 1 & Day 2 doses are 20 mg/m2. All subsequent days as specified, i.e. 20/27 mg/m2 means Cycle 1 Day 1 & Day 2 doses are 20 mg/m2 and all other days are 27mg/m2.

Additional cycles of therapy may be administered provided the subject meets all of the

following at the **beginning of each cycle**:

- ANC \geq 1,500/µL.
- Platelet count $\geq 100,000/\mu L$.
- All other Grade 2, 3 or 4 non-hematological toxicities have resolved as required in section 6.3.3.
- Serum creatinine $\leq 1.5 \text{ x}$ ULN OR measured or calculated creatinine clearance $\geq 60 \text{ mL/min}$ using the Cockcroft-Gault.

6.3 DOSE REDUCTIONS/ADJUSTMENTS

6.3.1 DOSE LEVELS

Carfilzomib – Phase I portion of the study

Starting Dose	Dose Level -1	Dose Level -2
$20/27 mg/m^2$	$20/20 mg/m^2$	Hold
$20/36 mg/m^2$	$20/27 mg/m^2$	$20/20 mg/m^2$
$20/45 mg/m^2$	$20/36 mg/m^2$	$20/27 mg/m^2$
20/56 mg/m2	$20/45 mg/m^2$	$20/36 mg/m^2$
20/70 mg/m2	$20/56 mg/m^2$	$20/45 mg/m^2$

Carfilzomib – Phase II portion of the study

Starting Dose	Dose Level -1	Dose Level -2
20/36 mg/m ²	20/27 mg/m ²	20/20 mg/m ²

* Cycle 1 Day 1 & Day 2 doses are 20 mg/m2. All subsequent days as specified, i.e. 20/27 mg/m2 means Cycle 1 Day 1 & Day 2 doses are 20 mg/m2 and all other days are 27mg/m2.

In the event that carfilzomib is held on Day 2, 8, 9, 15 and/or 16 of therapy, missed doses are not to be made up. All dose reductions are permanent and no dose re-escalation will be allowed on this trial.

Irinotecan- Phase I and II portions of the study

Starting Dose	Dose Level -1	Dose Level -2
125 mg/m2	100 mg/m ²	75 mg/m ²

*If Dose level -1 is utilized

In the event that irinotecan is held on Day 8 and/or Day 15, missed doses are not to be made up. All dose reductions are permanent and no dose re-escalation will be allowed on this trial.

6.3.2 DOSE REDUCTIONS FOR CARFILZOMIB AND IRINOTECAN HEMATOLOGIC TOXICITIES:

The following table outlines the dose reduction guidelines for carfilzomib and irinotecan for thrombocytopenia and neutropenia that occurs at any point during the prior cycle:

Event Name	Neutropenia			
Grade of Event	Recommended Action for Carfilzomib	Recommended Action for Irinotecan		
≤ Grade 1	No change in dose	No change in dose		
Grade 2	No change in dose	No change in dose		
Grade 3	No change in dose	Hold [*] until \leq Grade 2. Resume at one dose level lower, if indicated. ^{**}		
Grade 4	Hold [*] until \leq Grade 2. Resume at one dose level lower, if indicated. ^{**}	Hold [*] until \leq Grade 2. Resume at one dose level lower, if indicated. ^{**}		
*Subjects requiring a delay of >3 weeks should go off protocol therapy.				
**Subjects requiring > two dose reductions should go off protocol therapy.				
No prophylactic growth factor support is allowed in cycle 1, but growth factor support in the				
event of neutropenia is encouraged and should be administered at the discretion of the				
treating physician and per National Comprehensive Cancer Network Guidelines				
(http://www.nccn.org).				

Event Name	Thrombocytopenia	
Grade of Event	Recommended Action for	Recommended Action for

	Carfilzomib	Irinotecan
≤ Grade 1	No change in dose	No change in dose
Grade 2	No change in dose	No change in dose.
	No change in dose	Hold [*] until \leq Grade 2. Resume at
Grade 3		one dose level lower, if
		indicated.**
	Hold [*] until < Grade 2. Resume	Hold [*] until \leq Grade 2. Resume at
Grade 4	at one dose level lower, if	one dose level lower, if
	indicated.**	indicated.**
*Subjects requiring a delay of >3 weeks should go off protocol therapy.		
**Subjects requiring > two dose reductions should go off protocol therapy.		

6.3.3 DOSE REDUCTIONS OF CARFILZOMIB AND IRINOTECAN FOR NON-HEMATOLOGIC TOXICITIES

Dose adjustment guidelines for non-hematologic toxicities that occur at any point during the prior cycle are summarized as follows:

Event name	Recommended Action	Recommended Action
Grade of Event	Carfilzomib	Irinotecan
Allergic reaction/hypersensitivity		
Grade 2 – 3	Hold until ≤ Grade 1, reinstitute at full dose.	No change in dose
Grade 4	Discontinue	No change in dose
Tumor lysis syndrome $(\geq 3 \text{ of following:} \geq 50\% \text{ increase in creatinine, uric acid, or phosphate;} \geq 30\% \text{ increase in potassium;} \geq 20\% \text{ decrease in calcium; or } \geq 2-\text{fold increase in LDH}$	Hold carfilzomib until all abnormalities in serum chemistries have resolved. Reinstitute at full doses.	Hold irinotecan until all abnormalities in serum chemistries have resolved. Reinstitute at full doses.
Infection Grade 3 or 4	Hold carfilzomib until systemic treatment for infection complete. If no neutropenia, restart at full dose. If neutropenic, follow neutropenic instructions.	Hold irinotecan until systemic treatment for infection complete. If no neutropenia, restart at full dose. If neutropenic, follow neutropenic instructions.
Peripheral Neuropathy Grade 2 treatment emergent with pain or Grade 3neuropathy	Continue to dose. If neuropathy persists for more than two weeks hold carfilzomib until resolved to ≤ Gr 2 without pain. Then restart at 1 dose decrement if indicated.**	No change in dose
Peripheral Neuropathy Grade 4 neuropathy	Discontinue	Discontinue
Serum creatinine elevation Grade 2, 3 or 4	Hold until ≤ Grade 1. Resume at one dose level lower, if indicated.**	Hold until ≤ Grade 1. Resume at one dose level lower, if indicated.**

Hepatic Impairment Grade 3 or 4 elevation of transaminases or bilirubin	Hold Carfilzomib until < Grade 2. Resume at one dose level lower, if indicated.**	Hold Irinotecan until < Grade 2. Resume at one dose level lower, if indicated.**
Congestive heart failure Grade 3 or 4	Any subject with symptoms of grade 3 or 4 congestive heart failure, whether or not drug related, must have the dose held until resolution to grade 2 or less, or return to baseline, after which treatment may continue at 1 dose decrement, or the subject may be withdrawn from the study. If no resolution after 2 weeks, the subject will be withdrawn from the study.	No change in dose
Pulmonary Hypertension Grade 2, 3, or 4	Hold Carfilzomib until < Grade 2. Resume at one dose level lower, if indicated.**	No change in dose
Diarrhea		
Grade 2 or Grade 3 lasting < 3 days*	No change in dose	Hold Irinotecan until < Grade 2. Resume at same dose level.
Grade 3 (lasting > 3 days) or 4*	Hold Carfilzomib until < Grade 2. Resume at one dose level lower, if indicated.**	Hold Irinotecan until < Grade 2. Resume at one dose level lower, if indicated.**
*Recommended management: Loper onset, followed by 2 mg with each loo 16 mg/24 hours) Adjunct anti-diarrhe	amide antidiarrheal therapy dosage ose motion until diarrhea-free for 1 al therapy is permitted and should	schedule: 4 mg at first 2 hours (maximum dosage: be recorded when used.
Nausea/Vomiting		
Grade 2	No change in dose.	Hold Irinotecan until < Grade 2. Resume at same dose level.
Grade 3	No change in dose	Hold Irinotecan until < Grade 2. Resume at one dose level lower, if indicated.**

Grade 4	Hold Carfilzomib until < Grade 2. Resume at one dose level lower, if indicated. **	Hold Irinotecan until < Grade 2. Resume at one dose level lower, if indicated. **						
Other Non-Hematologic Toxicity								
Other non-hematologic toxicity assessed as drugrelated \geq Grade 3	Hold dose until toxicity resolves to < Grade 2 or baseline. Resume at one dose level lower, if indicated. **.	Hold dose until toxicity resolves to < Grade 2 or baseline. Resume at one dose level lower, if indicated. **.						
*Subjects requiring a delay of >3 weeks should go off protocol therapy. **Subjects requiring > two dose reductions should go off protocol therapy.								

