6.2 TREATMENT PLAN

6.2.1	PHASE I POR	FION OF THE STUDY	
ACENT	DOSE	DOUTE	D

AGENT	DOSE	ROUTE	DAYS	INTERVAL
Irinotecan	125 mg/m ²	IV infusion (over 90 min)	1, 8, 15	q 28 days
Carfilzomib	$20/*mg/m^2$	IV infusion (over 30 min)	1, 2, 8, 9 15 and 16	q 28 days

* Cycle 1 Day 1 & Day 2 doses are 20 mg/m2. All subsequent days as specified, i.e. 20/27 mg/m2 means Cycle 1 Day 1 & Day 2 doses are 20 mg/m2 and all other days are 27mg/m2.

Dosage schedule, phase 1b:

	Doses		
3+3 design	Carfilzomib*	Irinotecan	
Cohort -2	20 mg/m^2	75 mg/m^2	
Cohort -1	20 mg/m^2	100 mg/m^2	
Cohort 1	$20/27 \text{ mg/m}^2$	125 mg/m^2	
Cohort 2	20/36 mg/m ²	125 mg/m^2	
Cohort 3	$20/45 \text{ mg/m}^2$	125 mg/m ²	
Cohort 4	20/56 mg/m ²	125 mg/m^2	
Cohort 5	20/70 mg/m ²	125 mg/m^2	
* Cycle 1 Day 1 & Day 2 doses are 20 mg/m2. All subsequent days as specified,			

other days are 27mg/m2.

Additional cycles of therapy may be administered provided the subject meets all of the following at the beginning of each cycle prior to treatment on Day 1 (at most 2 days prior to Day 1 of the next cycle):

- ANC $\ge 1,500/\mu L$. •
- Platelet count $\geq 100,000/\mu$ L.

- All other Grade 2, 3 or 4 non-hematological toxicities have resolved as required in section 6.3.3.
- Serum creatinine ≤ 1.5 x IULN OR measured or calculated creatinine clearance ≥ 60 mL/min using the Cockcroft-Gault.

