6.3.5.2 Infections

Subjects with grade 3 or 4 active or suspected infections should have treatment withheld until infection has resolved and anti-infective treatment has been completed. After the infection has resolved and anti-infective treatment has been completed, treatment may continue at the original dose. If there is no resolution of toxicity after 3 weeks, the subject will be withdrawn from the study.

6.3.5.3 Congestive Heart Failure (CHF)

Any subject with symptoms of grade 3 or 4 CHF or any other suspected acute cardiac event, whether or not drug related, must have the dose held until resolution. After the event has resolved or returned to baseline, treatment may continue at 1 dose decrement, with the approval of the Medical Monitor, or the subject may be withdrawn from the study. If there is no resolution of CHF after 2 weeks, the subject will be withdrawn from the study.

6.3.5.4 Pulmonary Hypertension

Pulmonary arterial hypertension was reported in 2% of patients treated with carfilzomib and was Grade 3 or greater in less than 1% of patients. Evaluate with cardiac imaging and/or other tests as indicated. Unless otherwise specified in the individual protocol, withhold carfilzomib for pulmonary hypertension until resolved or returned to baseline and consider whether to restart carfilzomib based on a benefit/risk assessment.

6.3.5.5 Myocardial Infarction

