Death due to cardiac arrest has occurred within a day of carfilzomib administration. New onset or worsening congestive heart failure or myocardial ischemia have occurred following administration of carfilzomib. Cardiac failure events (e.g., cardiac failure congestive, pulmonary edema, and ejection fraction decreased) were reported in 7% of patients. Monitor for cardiac complications and manage promptly. Unless otherwise specified in the individual protocol, withhold carfilzomib for Grade 3 or 4 cardiac events until recovery and consider whether to restart carfilzomib based on a benefit/risk assessment. Patients with NYHA Class III and IV heart failure, myocardial infarction in the preceding 6 months, or conduction abnormalities uncontrolled by medications were not eligible for the clinical studies. These patients may be at greater risk for cardiac complications. Dyspnea, predominately Grade 1 and 2, was reported in 35% of subjects enrolled in clinical studies (see Section 6.7, Undesirable Effects). Evaluate patients with dyspnea based on the clinical presentation and manage accordingly. Unless otherwise specified in the individual protocol, reduce or interrupt dose as appropriate.

6.3.5.6 Hepatic Toxicity

Cases of hepatic failure, including fatal cases, have been reported (< 1%). Carfilzomib can cause elevations of serum transaminases and bilirubin. Monitor liver enzymes frequently. Please use section 6.3.3 as a guide to reduce or interrupt carfilzomib dose.

6.3.5.7 Posterior Reversible Encephalopathy Syndrome

Posterior reversible encephalopathy syndrome (PRES), formerly termed reversible posterior leukoencephalopathy syndrome (RPLS), is a rare, neurological disorder, which can present with seizure, headache, lethargy, confusion, blindness, altered consciousness, and other visual and neurological disturbances, along with hypertension. The diagnosis is confirmed by neuroradiological imaging. If diagnosed early and treated, the symptoms of PRES may be reversed. Cases of PRES have been reported in patients receiving carfilzomib. Discontinue carfilzomib if PRES is suspected. The safety of reinitiating carfilzomib therapy in patients previously experiencing PRES in not known.

6.3.5.8 Conditions Not Requiring Dose Reduction

The following conditions are exceptions to the above guidelines. Carfilzomib does not need to be held in the following cases:

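### After grade 3-4 heart failure, the Section 6.3.3 table permits carfilzomib restart at grade 2 with no approval step; Section 6.3.5.3 asks for resolution or baseline plus Medical Monitor approval, and nothing says which governs

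*Combined protocol and SAP*

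**What the plan says.** **Table in 6.3.3, CHF row.** A subject with grade 3 or 4 CHF, related to drug or not, "must have the dose held until resolution to grade 2 or less, or return to baseline". Carfilzomib may then continue one dose level lower, or the subject may be withdrawn. No approval is mentioned. The row ends: "If no resolution after 2 weeks, the subject will be withdrawn from the study".

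**Section 6.3.5.3.** The same event, again regardless of attribution, requires a hold until resolution. Then: "After the event has resolved or returned to baseline, treatment may continue at 1 dose decrement, with the approval of the Medical Monitor". The time limit matches the table: "If there is no resolution of CHF after 2 weeks, the subject will be withdrawn from the study". No grade is attached to resolution.

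**Cycle-start check.** To begin a further cycle in phase II, Section 6.2.4 requires that non-hematologic "toxicities have resolved as required in section 6.3.3". Section 6.2.1 has the same condition for phase Ib. Neither cites 6.3.5.

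**Section 6.3.5.5.** This gives a third wording for cardiac events: "Unless otherwise specified in the individual protocol, withhold carfilzomib for Grade 3 or 4 cardiac events until recovery".

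**The concern.** Two rules cover one event, and they differ on the restart threshold and on who must agree to the restart. A subject whose new heart failure has improved only to grade 2 meets the table's condition. Under 6.3.5.3 the same subject cannot be re-dosed without the Medical Monitor, and arguably cannot be re-dosed at all. The cycle-start check sends the site to the more permissive text.

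What is at stake is whether a patient with unresolved heart failure receives more carfilzomib without medical review. The protocol itself treats this as a recognised risk. Section 6.3.5.5 says: "Cardiac failure events (e.g., cardiac failure congestive, pulmonary edema, and ejection fraction decreased) were reported in 7% of patients". Section 9.3.1 places heart failure among the common effects.

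**Working it through.** The main check is a comparison of texts; the plan states no figure to reproduce.

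**1. CHF, grade 3 or 4**

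| Item | 6.3.3 table | 6.3.5.3 |
|---|---|---|
| Attribution | Related or not | Related or not |
| Restart threshold | Grade 2 or less, or baseline | Resolved or baseline; no grade given |
| Approval | None mentioned | Medical Monitor |
| Restart dose | One level lower | One level lower |
| Time limit | 2 weeks | 2 weeks |

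The rules agree on scope, restart dose and time limit. They differ on threshold and approval.

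**2. Who is caught.** A subject whose baseline was already grade 2 meets both thresholds by returning to it, so for that subject only approval differs. The threshold matters for a subject with a better baseline who develops grade 3-4 CHF and improves to grade 2. The table allows restart at 20/27 mg/m² (one level below 20/36, Section 6.3.1). Section 6.3.5.3 requires approval and can be read as requiring a continued hold, then withdrawal at 2 weeks.

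**3. Is there a precedence rule?** Elsewhere the protocol relates such texts to each other. Section 6.3.5.6 sends hepatic events to 6.3.3, 6.3.5.8 lists exceptions to the preceding guidelines, and 6.3.5.4 and 6.3.5.5 yield to other protocol text. Section 6.3.5.10 covers only modifications not already described. Nothing of this kind is attached to 6.3.5.3. Section 6.3.5.5 leans toward the stricter rule, but because it yields it cannot settle the matter.

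**4. Other rows of the table.** Pulmonary hypertension and hepatic impairment must fall below grade 2, and creatinine to grade 1 or less. Neuropathy may restart at grade 2 if painless. The CHF threshold is therefore looser than several neighbouring rows, but not the only one at grade 2.

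**5. Size.** The documents give no rate for the affected group. Assume the carfilzomib rates carry over to the 88 planned phase II registrations:

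- 7% (6.3.5.5): 0.07 × 88 = 6.2
- 10%, the upper edge of the common band (9.3.1): 0.10 × 88 = 8.8

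These are about 6 to 9 events of any grade. The affected group is a subset of them, possibly empty.

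**6. Effect on the design.** Section 11.3 counts as evaluable every eligible phase II subject who received at least one dose of each drug, and measures survival from registration to death. Restarting or stopping carfilzomib does not change that classification. The decision rules (22 of 40 and 15 of 40 alive at six months) stand.

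**7. Other grade 3-4 non-hematologic toxicity (minor)**

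| Item | 6.3.3 table | 6.3.5.9 |
|---|---|---|
| Attribution | Drug-related only | No limit |
| Restart threshold | Below grade 2, or baseline | Below grade 2 |
| Dose on restart | Each drug one level lower, if indicated | Irinotecan one level lower; no carfilzomib reduction named |
| Not resolved by 3 weeks | Off protocol therapy | Leaves the study |

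Section 8.1(d) treats a delay beyond 3 weeks as removal from protocol treatment, which agrees with the table.

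**The case against.** The best defence is that the texts can be read together. Section 6.3.3 presents itself as a summary of recommended actions, and 6.3.5 as additional information. A summary that omits an approval step does not waive one stated a few pages later. A site that follows 6.3.5.3 satisfies both texts, and 6.3.5.11 gives a contact for questions. The cycle-start check does not switch off 6.3.5.3 and does not govern restarts within a cycle. The phase Ib check no longer matters in practice, because Section 1.5 reports that enrollment to that part is complete.

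Much of this stands. It shows that a careful site can comply, but not that the threshold is settled, and the live phase II check still cites only the permissive text.

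A reader might infer that a subject still at grade 2 on day 14 must be withdrawn under 6.3.5.3. The documents do not support so firm a reading. Section 6.3.5.3 gives no grade for resolution, and the table is the only place that does. On a reading where the table defines the term, grade 2 counts as resolved in both texts and only approval differs. The stricter reading is plausible but not proven.

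On other toxicity, it is fair to say that sites could already dose differently under the table alone, since its reductions apply only if indicated. Section 6.3.5.9's silence on carfilzomib could also be filled from the table. That is why this part is secondary.

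**Conclusion.** The point holds as a dosing-safety inconsistency that should be corrected. For grade 3-4 CHF the protocol gives two restart rules, and the phase II cycle-start check refers only to the one without Medical Monitor approval. The approval difference is plain from the text. The threshold difference depends on what resolution means in 6.3.5.3, which the protocol leaves open.

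The number affected is unknown and may be zero. A reader might take 6 to 9 of 88 as the number at risk, but it is not. The 7% also covers pulmonary edema and reduced ejection fraction, with grade not stated. The common band also covers rhythm problems. Exclusion criterion 10 removes subjects with NYHA Class III or IV heart failure, so carry-over of either rate is uncertain.

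A reader might also infer that wording about leaving the study would cost survival follow-up and hence power. Section 8.2 follows all phase II subjects every 3 months, so this is only a risk of misreading. No design figure changes.

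**What to change.** 1. Amend the CHF row of the 6.3.3 table to the 6.3.5.3 rule: carfilzomib restarts one dose level lower only after CHF has resolved or returned to baseline, with Medical Monitor approval, and stops if this is not reached by 2 weeks. Removing the grade 2 threshold also removes the only text that supports reading grade 2 as resolved. This keeps a safeguard the protocol already contains.
2. Have the Section 6.2.4 cycle-start check cite 6.3.5 as well as 6.3.3.
3. Minor: have the clinical leads choose one rule for other grade 3-4 non-hematologic toxicity (attribution, baseline restart, which drug is reduced) and state it in both the table and 6.3.5.9. Choosing the table's version relaxes 6.3.5.9, so the reason should be recorded. Choosing 6.3.5.9 means holds and irinotecan reductions for events not judged drug-related.
4. Minor: wherever leaving the study is meant as stopping treatment (6.3.3 CHF row, 6.3.5.2, 6.3.5.3, 6.3.5.9), say off protocol therapy, consistent with 8.1(d) and 8.2.

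The cost is amendment wording and a site notice, with no added patients or procedures. The downside is that a few subjects may be held longer or withdrawn from treatment under the stricter CHF rule.

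### For Grade 3-4 congestive heart failure, Sections 6.3.3 and 6.3.5.3 set different release states and approval steps, so a partly recovered subject may be re-treated under one and must be withdrawn under the other

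*Combined protocol and SAP*

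**What the plan says.** **Section 6.3.3, congestive heart failure row (Grade 3 or 4), carfilzomib column.** The subject "must have the dose held until resolution to grade 2 or less, or return to baseline, after which treatment may continue". The options at that point are permissive: "treatment may continue at 1 dose decrement, or the subject may be withdrawn from the study". The row ends with a time limit: "If no resolution after 2 weeks, the subject will be withdrawn from the study". No approval step appears. The irinotecan column leaves that dose unchanged.

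**Section 6.3.5.3 (Congestive Heart Failure).** For the same grades, and also for other suspected acute cardiac events, a subject, "whether or not drug related, must have the dose held until resolution". Then: "After the event has resolved or returned to baseline, treatment may continue at 1 dose decrement, with the approval of the Medical Monitor"; withdrawal is the alternative. It also has a time limit: "If there is no resolution of CHF after 2 weeks, the subject will be withdrawn from the study". It does not name the drug held.

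**Section 6.3.5.5 (Myocardial Infarction).** A third wording, which applies only where the individual protocol does not specify otherwise: "withhold carfilzomib for Grade 3 or 4 cardiac events until recovery and consider whether to restart carfilzomib based on a benefit/risk assessment".

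**Sections 6.2.1 and 6.2.4.** Further cycles require, among other conditions, that non-hematologic toxicities have recovered to the extent that 6.3.3 demands.

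**The concern.** Two sections govern the same event with nearly the same opening words, yet they differ on how far the subject must recover and on who must agree to a restart. No sentence says which prevails for this event. The difference carries into the mandatory 2-week withdrawal, because each section ties that limit to its own notion of resolution.

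Safety and tolerability are a secondary endpoint, and at least 8 sites are planned. Section 6.3.5.5 itself reports death from cardiac arrest within a day of carfilzomib. If re-exposure, approval and withdrawal after Grade 3-4 heart failure depend on which section a site follows, cardiac safety data and treatment exposure will not be comparable across sites. Nor can a monitor say which conduct is a protocol deviation.

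**Working it through.** No figure in the plan depends on this point, so there is nothing to reproduce. The check is a side-by-side reading.

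| Element | 6.3.3 table | 6.3.5.3 |
|---|---|---|
| Event | Grade 3-4 heart failure | The same, plus other suspected acute cardiac events |
| Release state | Grade 2 or less, or baseline | Resolved, or baseline |
| Approval | None stated | Medical Monitor |
| Dose on restart | One decrement | One decrement |
| Mandatory withdrawal | No resolution after 2 weeks; the row defines resolution as Grade 2 or less | No resolution after 2 weeks; no grade attached |

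**Subject's state at 2 weeks:**

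1. *Grade 2 or less, not resolved and still worse than baseline.* The table's release condition is met, so re-treatment is permitted. The condition in 6.3.5.3 is not met on its wording, so withdrawal is mandatory. The rules conflict.
2. *Resolved or back at baseline.* Both permit continuation at one decrement, but only 6.3.5.3 requires approval. The rules differ on approval.
3. *Still Grade 3-4 and worse than baseline.* Both require withdrawal. The rules agree.

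**Does another section settle it?**

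- *Cycle-start criteria (6.2.1, 6.2.4).* These apply on Day 1 of a cycle, whereas carfilzomib is given on Days 1, 2, 8, 9, 15 and 16 of 28. Assume the 2 weeks run from the start of the hold, which neither section says. A hold starting on Day 1 then reaches the limit on Day 1 + 14 = Day 15, a dosing day within the same cycle, where the cycle-start criteria do not apply. A hold starting on Day 15 reaches it on Day 29, which is Day 1 of the next cycle, where they do. Both situations can arise.
- *Deferral to the table.* Section 6.3.5.6 (hepatic toxicity) sends the reader to 6.3.3. Section 6.3.5.3 does not.
- *Investigator discretion (6.3.5.10).* This covers only modifications not already described. Heart failure is described twice.
- *Contact for questions (6.3.5.11).* A contact for modification queries is not an approval step.
- *Section 6.3.5.5.* It yields to the individual protocol, so it leads back to the two differing rules.

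**The case against.** The strongest reply is that the sections can be read together. The table calls its entries recommended actions and a summary, and 6.3.5 is headed as additional information. Because the table only permits continuation and also allows withdrawal, a site that holds longer, seeks approval or withdraws under 6.3.5.3 breaches nothing in 6.3.3. In addition, 6.2.1 and 6.2.4 tie recovery at cycle start to 6.3.3, so resolution in 6.3.5.3 could be read in the table's sense, which would remove the conflict at 2 weeks.

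Part of this stands. The table does not compel re-treatment, so a reader who infers that the same subject is re-dosed under one section and withdrawn under the other goes too far: the subject *may* be re-dosed under the table. But a site that follows the table alone can breach 6.3.5.3, and nothing tells it that the table is incomplete for this event. Carrying the Grade 2 threshold into 6.3.5.3 has no support in that section's wording, and doing so would still leave the approval step unreconciled.

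Three other inferences are tempting but not supported:

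- *Drug and scope as further contradictions.* Section 6.3.5.3 is silent on the drug, and silence does not contradict the irinotecan column. Its wider event list is added coverage; 6.3.5.5 and the table's row for other drug-related toxicity also bear on cardiac events. Both need clarifying, but neither is a conflict.
- *No Medical Monitor exists.* Contact pages were removed from the public text, so the absence of a named role there proves nothing.
- *About 6 subjects are affected.* Section 6.3.5.5 states: "Cardiac failure events (e.g., cardiac failure congestive, pulmonary edema, and ejection fraction decreased) were reported in 7% of patients". Multiplying gives 0.07 × 88 = 6.2. The rate has no grade limit, includes pulmonary edema and reduced ejection fraction, and describes carfilzomib patients in general. It is not the number who meet the conflict.

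**Conclusion.** The inconsistency is real and narrow. Outcomes can be opposed only for a subject with Grade 3-4 heart failure who at 2 weeks is at Grade 2 or less but neither resolved nor at baseline: re-treatment is permitted under 6.3.3 and withdrawal is mandatory under 6.3.5.3 as worded. For every other re-treated Grade 3-4 case, the texts differ on whether Medical Monitor approval is needed. For a subject still at Grade 3-4 and worse than baseline at 2 weeks, they agree.

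The number of subjects affected cannot be derived: the documents give neither the Grade 3-4 share of cardiac failure events nor the share partly recovered at 2 weeks. The conclusion rests on the ordinary meaning of resolution in 6.3.5.3, which is not defined there. It takes no view on which rule is clinically right. Because the point concerns re-exposure after a serious cardiac event and is cheap to correct, it should be corrected.

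**What to change.** Reconcile 6.3.3 and 6.3.5.3 into one rule, stated once and cross-referenced from the other place, and align the recovery wording in 6.3.5.5 with it. The rule should:

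- use one release state for both restart and the 2-week limit;
- state explicitly whether Medical Monitor approval is required;
- clarify which drug or drugs are held;
- clarify whether other acute cardiac events are covered.

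The sponsor's clinicians decide the content. The cost is amendment wording and a notice to sites; sample size, endpoints and analyses do not change.
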